6.0 Subject Recruitment

Subjects will be recruited through referring community mental health centers, treatment providers, invited to participate if they are included in our registry, and self-referrals through advertisement and word-of-mouth.

7.0 Study Procedures

See Study Procedures Table (Attachment 1)

8.0 Clinical Assessments and Procedures

The following assessments will be administered at one or more visits during the duration of the study according to the study procedures tables (Attachment 1). All assessments will be completed by study personnel based on interviews with the subject or based on questionnaires completed by the subject.

Diagnostic Interviews

The Structured Clinical Interview for DSM-IV-TR (SCID-I/P Patient Edition) will be used to confirm the diagnosis of Axis I disorders and rule out schizophrenia or a related psychotic disorder or bipolar I disorder (18). The SCID-IP is a semi-structured interview designed to evaluate DSM-IV-TR Axis I diagnoses.

The Structured Clinical Interview for DSM-IV AXIS II (SCID-II) Personality Disorders Version will be used to confirm a borderline personality disorder diagnosis (17).

The Brief Psychiatric Rating Scale (BPRS)

The BPRS is an 18-item scale measuring positive symptoms, general psychopathology and affective symptoms (19). Some of the items (e.g. mannerisms and posturing) can be rated simply on observation of the subject; other items (e.g. anxiety) involve an element of self-reporting by the subject.

Clinical Global Impressions Severity Scale (CGI-S)

The CGI-S will be used for repeated evaluations of global psychopathology (20-21). The CGI-S scale is widely used in schizophrenia research and is a single 7-point Likert scale rating severity of psychopathology on a scale of 1 (normal, not ill) to 7 (very severely ill).

Clinical Global Impressions Severity Improvement Scale (CGI-I)

The CGI-I is used to assess the clinical change as compared to symptoms at baseline using a 7-point Likert scale, ranging from very much improved (1) to very much worse (7) (20-21).

Interview for Traumatic Events in Childhood (ITEC)

The ITEC aims to assess multiple types of childhood traumatic events, including sexual abuse, physical abuse, emotional abuse, and neglect (22). The ITEC utilizes an empirically based scoring system for determining the severity of traumatic events. Each subscale yields a composite score indicating the severity of maltreatment. An abbreviated version may be used at the discretion of the principal investigator.

Indiana Psychiatric Illness Interview (IPII)

The IPII is a semi-structured interview developed to assess illness narratives. Study personnel conduct the interview, which typically lasts between 30 and 60 minutes (26). Responses are audio taped and later transcribed. The interview is divided conceptually into four sections. First, rapport is established and subjects are asked to tell the story of their lives in as much detail as they can. Second, subjects are asked if they think they have a mental illness and how they understand it. This is followed with questions about what has and has not been affected by their condition in terms of interpersonal and psychological life. In the third section, subjects are asked if and how their condition “controls” their life and if and how they

“control” their condition. Fourth, subjects are asked what they expect to stay the same and what will be different in the future.

Borderline Personality Disorder Severity Index (BPDSI)-90 day Version

The BPDSI is a semi-structured clinical interview assessing the frequency and severity of manifestations of Borderline Personality Disorder during a circumscribed period of three months. All frequency questions are scored on 10-point scales (0 = never; 10 = daily). This also applies to the items where such a high frequency is unlikely (14).

Borderline Personality Disorder Severity Index (BPDSI)-7 day Version-Modified

The BPDSI is a semi-structured clinical interview assessing the frequency and severity of manifestations of Borderline Personality Disorder during a circumscribed period of the previous 7 days. All frequency questions are scored on 7-point scales (0 = never; 7 = daily). This also applies to the items where such a high frequency is unlikely. This modified version was created with the developer of the BPDSI, [name]. The modified 7 day version will be used as one measurement of BPD symptom changes during the course of the study (14).

Symptom Checklist-90-R (SCL-90-R)

The SCL-90-R instrument helps evaluate a broad range of psychological problems and symptoms of psychopathology. The instrument is also useful in measuring patient progress or treatment outcomes. The SCL-90-R contains 90 items on a 5-point rating scale yielding nine scores along primary symptom dimensions and three scores among global distress indices (16).

BPD Checklist

The BPD Checklist is a DSM-IV based self-report questionnaire, designed to assess the experienced burden of specific BPD symptoms during the previous month (23).

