3.0 Specific Aims

Specific aim 1: to evaluate whether mifepristone will produce rapid symptom reduction after seven days of active treatment, as measured by Borderline Personality Disorder Severity Index (BPDSI) total score. Further, to evaluate whether seven days of mifepristone treatment will result in a durable improvement in symptoms persisting after active treatment discontinuation, as measured by Borderline Personality

Disorder Severity Index (BPDSI) total score.

Specific aim 2: to evaluate safety and tolerability of mifepristone

Specific aim 3: to assess cortisol levels as a potential biomarker of HPA-axis engagement.

Exploratory Aims: to assess clinical and demographic moderators of response to mifepristone, including childhood abuse characteristics (e.g., type of abuse, age of onset, duration) and comorbid psychiatric illnesses.

Outcome Measures: The primary outcome measures will be the Borderline Personality Disorder Severity Index (BPDSI) total score. With this measure, we will be able to investigate specifically the effect of mifepristone on BPD's entire psychopathologic spectrum. For inclusion, all subjects must demonstrate a minimum severity of a total score ≥ 3 on the CGI-S. Secondary outcomes will include the BPDSI symptom domain subscales, the Brief Psychiatric Rating Scale (BPRS), the self-report Borderline Checklist, the Symptom Checklist-90-Revised (SCL-90-R), improvement in metacognitive capacity, and the Clinical Global Impressions-Severity (CGI-S) and Clinical Global Impressions-Improvement (CGI-I) measures. Clinical assessments will be performed by trained raters, who will be blind to subjects' treatment condition.

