16.0 Statistical Considerations

Continuous variables will be summarized by treatment groups using descriptive statistics including mean, standard deviation, and range. Categorical variables will be summarized using frequency counts and percentages. Baseline clinical and demographic data will be compared between the two treatment groups to assess the effectiveness of the randomization. Dichotomous and ordinal variables will be examined using chi-square tests and continuous measures with Student's t-tests. Appropriate exact and non-parametric methods will be used as needed. The primary goal of this study will be to estimate the effect size for the treatment on the BPDSI total score. This will be done at each time point, as we are also interested in how the effect is sustained after active drug treatment is discontinued. We also will graph the trajectory of each subject over time. Supportive analyses will be based on the linear mixed effects model with a random subject effect for BPDSI with time, treatment and time by treatment interaction as covariates. The model parameters will be estimated using SAS MIXED procedure and the p-values for the comparisons of the differential treatment effects and 95% confidence interval for the treatment effect will be reported. The time by treatment interaction will be assessed to examine whether the active drug effect was changing over time. Secondary outcomes and serum cortisol levels will be examined similarly. Graphs, Pearson or Spearman correlations, and linear mixed models will be used to examine the relationship between serum cortisol levels and outcome measures. Due to the small sample size, covariates (type of abuse, age of abuse onset, abuse duration, diagnosis of MDD, diagnosis of PTSD) will be examined graphically. Safety analyses of this study will include summarized counts and rates per treatment group of the incidence of the adverse events. Incidences of selected adverse events from the two treatment arms will be compared using the Fisher's exact test on an exploratory basis.

Sample Size Justification: This is a pilot study designed to estimate effect sizes for a future randomized trial. It is recommended that a minimum of 12 subjects per group be used for this purpose based on estimating the precision of the meant treatment effect and variance (13).

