21. Guy W. ECDEU assessment manual for psychopharmacology. Washington, DC: US Department of Health, Education, and Welfare;338:534-537. 1976.
22. Lobbestael, Arntz, Harkema-Schouten, & Bernstein (2009). Development and psychometric evaluation of a new assessment method for childhood maltreatment experiences: The Interview for Traumatic Events in Childhood (ITEC). *Child Abuse & Neglect*, 33, 505–1517.
24. Mifeprex [package insert]. Danco Laboratories, New York, NY, 2009..
25. Korlym [package insert]. Corcept Therapeutics Inc., Menlo Park, CA, 2000.

ATTACHMENT 1
Study Procedures Table

Visit	1	2	3	4	5	6
Day		0	4	7	14	28
Visit Window (days since last visit)		14-30	4	3	7	14
Informed Consent	X					
SCID I & II	X					
Medical History	X					
Demographics	X					
Physical Exam	X					
Vitals	X	X	X	X	X	X
Verification of Preg Prevention	X	X	X	X	X	X
ECG ^a	X	X	X	X	X ^b	X ^b
CGI-S/I	X ^c	X ^c		X	X	X
BPRS		X		X	X	X
BPDSI (90-day)	X					
BPDSI (7-day)		X		X	X	X
BPD Checklist		X		X	X	X
ITEC ^d	X					
SCL-90-R		X		X	X	X
IPII		X				X
CBC	X					
CMP	X	X		X	X	X
Serum Preg test (beta HCG)	X					
Blood Cortisol Level		X		X ^e	X ^e	X ^e
Biobank Blood Sample		X				X
Pharmacokinetics ^f				X		
Urine Pregnancy Test	X	X	X	X	X	X
Adverse Events			X	X	X	X
Concomitant Medication		X	X	X	X	X
Medication Dispensation		X				
Medication Accountability			X ^g	X		

a Triplicate tracings to be collected at least 1 minute apart

b Subsequent ECG tracings will be collected at V5 and V6 at the discretion of the principal investigator

c CGI-I will not be completed at Visits 1 or 2 as there is no "improvement" score at baseline.

d Clinician may use abbreviated version of form, at principal investigator's discretion

e Subsequent blood collection to occur at the exact time of day as the baseline value (+/- 30 minutes)

f Pharmacokinetic analysis will be completed based off of time of study drug from previous day.

g Study medication will be reviewed during this visit for compliance purposes. Study medication will not be returned or dispensed at this visit

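### The BPD Checklist asks about the past month, so its Day 7 and Day 14 scores mostly or about half describe time before the first dose, and its by-visit effects cannot be read as the drug's time course

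*Combined protocol and SAP*

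**What the plan says.** Section 3.0 lists "the self-report Borderline Checklist" among the secondary outcomes. Section 8.0 describes it as "designed to assess the experienced burden of specific BPD symptoms during the previous month (23" (the trailing number is the reference). The row in Attachment 1, "BPD Checklist X X X X", marks Visits 2, 4, 5 and 6, which are Days 0, 7, 14 and 28. The same table dispenses medication only at Day 0, and section 4.0 sets treatment at seven days followed by follow-up.

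For the BPDSI total score, section 16.0 plans an effect size at each time point because "we are also interested in how the effect is sustained after active drug treatment is discontinued". It adds a supportive mixed model: "The time by treatment interaction will be assessed to examine whether the active drug effect was changing over time". It then states: "Secondary outcomes and serum cortisol levels will be examined similarly".

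For the BPDSI the plan matches recall to visit spacing. The 90-day version is used only at screening, and a modified version, covering "manifestations of Borderline Personality Disorder during a circumscribed period of the previous 7 days", is used at Days 0, 7, 14 and 28. No shortened recall, restriction to one visit or note on overlap is given for the Checklist.

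**The concern.** When the recall period is longer than the time since the first dose, part of each score describes untreated time. That part shrinks from visit to visit, so the between-arm difference on the Checklist can change simply because the window slides forward. The planned interaction cannot separate this from a real change in the drug effect.

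The error can go either way. A steady effect would seem to build up. An effect that ended with treatment would still be inside the window at Day 28 and could look sustained. The trial is asking about rapid versus durable benefit, and the Checklist results would stand beside the 7-day BPDSI results at the same visits as though both covered the same periods.

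**Working it through.** The plan gives no figure for the overlap, so there is none to reproduce.

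**Inputs from the documents.** Recall of one month (section 8.0); visits at Days 0, 7, 14 and 28 and dispensing at Day 0 (Attachment 1); seven days of treatment (section 4.0); 12 per arm (section 16.0).

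**Assumptions.** A month is L = 28, 30 or 31 days. The first dose is on Day 0, with Day 1 as a check. Recall weights, effect sizes and between-visit correlations are mine; the documents give none.

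**1. Share of the window before the first dose** = max(0, L − d)/L at visit day d.

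| L | Day 7 | Day 14 | Day 28 |
|---|---|---|---|
| 28 | 21/28 = 75.0% | 14/28 = 50.0% | 0% |
| 30 | 23/30 = 76.7% | 16/30 = 53.3% | 2/30 = 6.7% |
| 31 | 24/31 = 77.4% | 17/31 = 54.8% | 3/31 = 9.7% |

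With L = 30, the Day 7 form therefore shares 23 of its 30 days with the baseline form. A first dose on Day 1 raises the ranges to 78.6-80.6%, 53.6-58.1% and 3.6-12.9%. With a 7-day recall the share is 0% at all three visits.

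**2. Fraction of the true effect that is seen (L = 30).**

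- Equal weights, effect constant from Day 0: d/30, that is 7/30, 14/30 and 28/30.
- Equal weights, effect in Days 0-7 only: all seven days stay inside every window, so 7/30 each time.
- Recency weighting with half-life h, constant effect: (1 − 2^(−d/h)) / (1 − 2^(−30/h)). For h = 14 at Day 7: (1 − 0.707)/(1 − 0.226) = 0.379.
- Recency weighting, Days 0-7 only: (2^(−(d−7)/h) − 2^(−d/h)) / (1 − 2^(−30/h)).

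| Recall weighting | Constant effect: Day 7, 14, 28 | Ratio Day 28 / Day 7 | Days 0-7 effect: Day 7, 14, 28 |
|---|---|---|---|
| Equal | 0.233, 0.467, 0.933 | 4.0 | 0.233, 0.233, 0.233 |
| Half-life 14 days | 0.379, 0.646, 0.970 | 2.6 | 0.379, 0.268, 0.134 |
| Half-life 7 days | 0.527, 0.791, 0.988 | 1.9 | 0.527, 0.264, 0.066 |

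A 7-day recall with equal weights would give 1, 1, 1 and 1, 0, 0 for the two cases.

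**3. How often a steady effect would be declared to change.** For a Day 7 versus Day 28 contrast, the spurious rise is the true effect times the difference between the two fractions. For 0.5 SD this is 0.5 × (0.933 − 0.233) = 0.35 SD with equal weights and 0.231 SD with a 7-day half-life. For 0.8 SD it is 0.56 and 0.369 SD. The SD of the within-subject difference is √(2(1 − ρ)), so the noncentrality is rise / [√(2(1 − ρ)) × √(2/12)]. For 0.35 SD and ρ = 0.5 it is 0.35/0.408 = 0.857. With 22 degrees of freedom and two-sided 5%:

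| True effect, weighting | ρ = 0.3 | ρ = 0.5 | ρ = 0.8 |
|---|---|---|---|
| 0.5 SD, equal | 10.7% | 13.0% | 25.4% |
| 0.5 SD, half-life 7 days | 7.4% | 8.4% | 13.7% |
| 0.8 SD, equal | 19.9% | 25.9% | 54.5% |
| 0.8 SD, half-life 7 days | 11.3% | 13.9% | 27.7% |

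If recall matched the visit, the rate would be 5%.

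**The case against.** The best reply is that the plan already uses a suitable instrument where the time course matters. Aim 1 is defined on the BPDSI alone, with 7-day recall, and the sentence about a sustained effect concerns the BPDSI. The Checklist is reached only by a one-line carry-over, and the mixed model is called supportive. This stands, and it limits the point to one secondary scale.

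Second, pre-dose days are common to both randomised arms. With no drug effect there is no false difference and no false interaction; early dilution pulls toward no difference. This also stands. The rejection rates above are not false-positive rates under no effect; they apply when a real, constant effect exists. They also use a two-visit contrast that the plan does not name.

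Third, the flat pattern for a Days 0-7 effect needs equal weighting of all recalled days. Under recency weighting the effect visibly fades, although 7-13% of it would still show at Day 28. The false growth of a constant effect, by contrast, survives every weighting tried.

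Fourth, with 12 per arm the 95% half-width for a standardised difference is about 2.074 × √(2/12) = 0.85 SD, so a distortion of 0.23-0.35 SD lies well inside the noise. That is true of any one result. But the study exists to estimate effect sizes for a later trial, and imprecision does not make a systematic distortion harmless.

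Finally, the questionnaire form is not in the documents, so the recall period rests on section 8.0's description. Nothing there suggests a shorter one.

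**Conclusion.** The point holds. The overlap of 75-77%, 50-55% and 0-10% at Days 7, 14 and 28 follows from the stated recall and visit days, and no reasonable definition of month or first-dose time changes the conclusion. Whenever the drug has an effect, the Checklist's by-visit estimates and interaction mix that effect with the moving window. A constant effect would seem to grow 1.9- to 4.0-fold between Day 7 and Day 28, depending on the assumed recall weighting.

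The consequence is moderate: a planned analysis of one secondary scale would mislead as written, while the primary outcome, Aim 1 and the sample size are untouched.

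**What to change.** Add to section 16.0:

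> Because the BPD Checklist covers the previous month, its between-arm comparison will be made at Day 28 only. Days 7 and 14 will be reported descriptively with the recall overlap noted, and no time-by-treatment test will be done for this scale. The Day 28 window combines about 7 treatment days with about 21 post-treatment days, so it cannot separate rapid from durable benefit.

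This takes a few sentences and changes no visit, form or subject burden. The cost is two fewer inferential comparisons on one secondary scale. It does not recover what the long recall loses: the remaining Day 28 comparison still cannot tell rapid from durable benefit, and that question stays with the 7-day BPDSI.

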9.0 Safety Assessments and Procedures

Vitals

Vital signs will be assessed at study visits per Study Procedures Table (Attachment 1). Blood pressure and heart rate will be taken in a seated or supine position after a rest period of five minutes.

Medical History

The subject’s lifetime medical history will be taken during the screening period. Medical history includes previous and current diseases.

Physical Examination

A physical examination will be performed including a neurological examination.

Electrocardiograph (ECG)

Triplicate supine, 12 lead ECGs will be performed according to the Study Procedures Table (Attachment 1).

10.0 Laboratory Assessments

Laboratory assessments (blood and urine) will be collected at time points specified in Study Procedures Table (Attachment 1) and analyzed by a local laboratory with the exception of the urine dipstick

assessments which will be collected and analyzed onsite.

A total of ~16ml of blood will be collected for screening assessments (Visit 1), ~28ml will be collected at baseline (Visit 2), ~17ml will be collected at Day 7 (Visit 4), ~12ml will be collected at Day 14 (Visit 5), and ~22ml will be collected at Day 28 (Visit 6).

Laboratory assessments to be completed:

Complete Blood Count with differential (CBC w/diff)
Comprehensive Metabolic Panel (CMP)
Pregnancy testing: serum and urine
Cortisol (must be drawn +/- 30 minutes of initial Visit 2 draw time)
Pharmacokinetics
Optional Biobank blood sample

Pharmacokinetics

Six ml of blood will be collected for trough mifepristone plasma concentration analysis (sent for analysis to MicroConstants in San Diego, CA).

Optional Biobank Blood Sample

An additional 10ml of whole blood will be collected (at Visit 2 and Visit 6) and sent to the Indiana Clinical and Translational Sciences Institute (CTSI) from all subjects who sign a separate consent and will be stored for later analyses, such as genetic examination. Subjects may refuse to participate in the repository without consequence to their participation in the main study. Non-identifying demographic information will be submitted to the CTSI at the time of sample submission. Subjects will be able to request sample destruction from the CTSI repository by formal request to the main study site.

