4.0 Study Design

This is a single site safety and proof of concept study conducted at the Indiana University Psychotic Disorders Program. Twenty four subjects with borderline personality disorder will be randomized 1:1 to double-blind treatment with oral mifepristone or matched placebo for duration of seven days, with a follow up period.

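### The Visit 2 cortisol draw has no common clock window, and no draw-time term or log scale is planned, so between-subject analyses of cortisol levels carry avoidable time-of-day variation

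*Combined protocol and SAP*

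**What the plan says.** Section 3.0 makes cortisol the only measure named in its third aim: "to assess cortisol levels as a potential biomarker of HPA-axis engagement".

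Section 10.0 states the sampling rule as "Cortisol (must be drawn +/- 30 minutes of initial Visit 2 draw time". Footnote e of Attachment 1 says the same for Visits 4, 5 and 6: "Subsequent blood collection to occur at the exact time of day as the baseline value (+/- 30 minutes". Neither place, nor any other, gives a clock hour or window for the Visit 2 draw itself.

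Section 16.0 treats cortisol by analogy with the BPDSI: "Secondary outcomes and serum cortisol levels will be examined similarly". For the BPDSI, the main analysis is an effect size at each time point. The supportive analysis is a "linear mixed effects model with a random subject effect for BPDSI with time, treatment and time by treatment interaction as covariates". Section 16.0 also plans Pearson or Spearman correlations and mixed models relating serum cortisol levels to outcome measures. For cortisol it names no draw-time covariate, no log scale and no change-from-baseline measure.

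**The concern.** By requiring a 30-minute match, the protocol accepts that cortisol depends on the hour of the draw. It controls that hour within a subject and leaves it free between subjects. One subject may be sampled at 08:00 throughout and another at 16:00 throughout.

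Matching to a subject's own baseline hour does nothing for an analysis that compares levels across subjects, and two of the planned cortisol analyses do this: the arm effect size at each visit, and the correlation of levels with outcomes. Hour of draw then adds to the between-subject spread. At stake are the precision of the Aim 3 estimates and the strength of any cortisol-outcome relationship. Also at stake is whether an effect size from this pilot carries over to the later trial that it is meant to inform.

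**Working it through.** **Inputs from the documents.** Section 4.0: "Twenty four subjects with borderline personality disorder will be randomized 1:1 to double-blind treatment". Section 16.0: "It is recommended that a minimum of 12 subjects per group be used for this purpose". Later draws fall within 30 minutes of the subject's own Visit 2 time.

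**Inputs assumed.** The documents give no cortisol SD, no diurnal slope and no range of visit hours. I take draws spread uniformly over 8 hours (08:00 to 16:00), a linear fall of 4, 8 or 10 units over those hours, and a between-subject SD of 4 units at a fixed hour. A log-scale check (step 3) uses a second set of assumptions.

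**Step 1. The plan's own figure.** 2 × 12 = 24 agrees with Section 4.0. The 12 per group is a rule of thumb with no alpha, power or SD, so it cannot be derived. It gives a 95% half-width for a difference in means of t(0.975, 22) × √(2/12) = 0.85 SD. Anything that inflates the SD widens this in proportion.

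**Step 2. Levels.** SD due to draw hour = fall/√12. Variance ratio = 1 + (that SD)²/4². The SE ratio is its square root. A Pearson correlation with an outcome unrelated to draw hour is multiplied by 1/(SE ratio).

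| Assumed fall over 8 h | SD from draw hour | Variance ratio | SE ratio | Correlation multiplied by |
|---|---|---|---|---|
| 4 units | 1.15 | 1.08 | 1.04 | 0.96 |
| 8 units | 2.31 | 1.33 | 1.15 | 0.87 |
| 10 units | 2.89 | 1.52 | 1.23 | 0.81 |

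**Step 3. Levels against change, log scale.** Assume that cortisol halves over 8 hours (slope ln 2/8 = 0.0866 per hour), with log SD 0.3 between and 0.2 within subjects. The 30-minute tolerance, taken as uniform, adds 0.289 h × 0.0866 = 0.025.

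- Level, common hour: √(0.3² + 0.2² + 0.025²) × √(2/12) = 0.147.
- Level, 8-hour spread: draw hour adds 2.31 × 0.0866 = 0.200, so √(0.3² + 0.2² + 0.025² + 0.200²) × √(2/12) = 0.169.
- Change from Visit 2: the subject's own hour cancels, so √(0.2² + 0.2² + 0.025²) × √(2/12) = 0.116 at any spread.

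A simulation of 20,000 trials with 12 per arm agrees. The SE for change was 0.116 with a common hour and 0.115 with an 8-hour spread. Power for a 1.25-fold effect fell from 30% to 24% for levels and stayed at 45% for change. With no drug effect, the mean arm difference was about zero and the type I error was 0.046 to 0.051 at every spread.

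**Step 4. Raw scale with a proportional effect.** If the level falls from 14 to 6 units, a true doubling shows as +14 in a morning subject and +6 in an afternoon one. Under the step 3 assumptions, the mean of the declining level over 8 hours is (1 − 0.5)/ln 2 = 0.72 of its value at the start. A doubling averages 1.07 units if everyone is drawn at the start hour and 0.77 units over the 8-hour spread, which is 28% lower. Raw change from Visit 2 gives the same two figures, so subtracting the baseline does not remove this.

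**The case against.** The case for leaving the plan alone has real substance.

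- **No confounding.** A reader might infer that time of day is mixed up with the drug effect. The documents do not support that. Allocation is randomised 1:1 and treatment is double-blind, so the expected difference in draw hour between arms is zero. The simulation in step 3 shows no bias. This point stands in full.
- **Chance imbalance is not a second harm.** With an 8-hour spread, the mean draw hour differs between arms of 12 with an SD of 2.31 × √(2/12) = 0.94 h. At 1 unit per hour that is 0.94 units of arm difference, which a reader might add to the SE inflation. It is the same quantity: the fixed-time SE is 4 × √(2/12) = 1.63, and √(1.63² + 0.94²)/1.63 = 1.15, the ratio already in the table.
- **Correlations are weakened, not distorted.** Nothing in the documents suggests that draw hour tracks symptoms, so the expected effect is attenuation.
- **The protocol already protects within-subject change.** The 30-minute rule and the random subject effect take out a constant additive offset, so the time-by-treatment contrast is largely safe. That holds, but the mixed model is only supportive, and the effect sizes at each visit and the correlations do not have this protection if they are run on levels.
- **The scale is not fixed.** Section 16.0 commits neither to raw nor to log cortisol, and it allows non-parametric methods. The raw-scale point is therefore conditional on an untransformed analysis and a proportional effect. The background text expects a two- to three-fold rise, but in central cortisol, so proportionality in serum is plausible rather than established.
- **A large effect would show anyway.** Under the step 3 assumptions, power for a doubling on levels is 99.5% with a common hour and 97.5% with an 8-hour spread. That matters less in a pilot whose purpose is to estimate effect sizes.

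**Conclusion.** The point holds as a cheap improvement, not as a flaw that undermines Aim 3. Draw hour is uncontrolled between subjects, and no planned term accounts for it. Following the plan on cortisol levels therefore loses precision in the per-visit arm effect sizes and weakens the correlations with outcomes.

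The SE for levels rises by about 4% to 23% and correlations shrink to between 0.96 and 0.81 of their value, given an 8-hour uniform spread, falls of 4 to 10 units and a fixed-time SD of 4. Under the separate log-scale assumptions, the SE for levels rises from 0.147 to 0.169, while that for log change from Visit 2 stays at about 0.116. If the effect is proportional and cortisol is analysed untransformed, the effect size also depends on which hours were booked. That limits its use in planning the next trial.

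That the window and the draw-time term are missing is certain from the text. The size is not: every magnitude rests on assumed values, and if visits in practice cluster in a narrow part of the day the loss would be small.

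**What to change.** In Section 10.0 and footnote e of Attachment 1:

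- Set one common clock window for the Visit 2 cortisol draw in all subjects. Choose it to be compatible with the Visit 4 trough pharmacokinetic sample, which footnote f ties to the previous day's dose time.
- Keep the 30-minute match at Visits 4 to 6.
- Record the actual draw time at every visit.

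In Section 16.0:

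- Prespecify, for all subjects, log cortisol change from Visit 2 (or log cortisol adjusted for the Visit 2 value) as the Aim 3 measure.
- Include draw time as a covariate in any analysis of cortisol levels, including their relationship with outcomes.

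The analysis rules should apply whether or not everyone meets the window. If the log scale or the covariate came in only when a subject fell outside it, scheduling would choose the analysis.

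The cost is a few sentences and less freedom in booking the blood draws at four visits. Attachment 1 eases this, since splitting a visit's procedures is not counted as a deviation. No extra blood or visits are needed.
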